#### 3.3.1.2.2 Number of new and/or enlarging T2 lesions

Number of new and/or enlarging T2 hyperintense lesions over the study period will be analyzed using a negative binomial regression model with robust variance estimation in the ITT population. The robust variance can be estimated by specifying the participant identifier in the repeated statement using SAS PROC GENMOD (version 9.4 or later). The model will include the total lesion count across all magnetic resonance imaging (MRI) scans at all scheduled post-randomization visits during the study period as the response variable, with treatment group, age at screening (>40,  $\leq$ 40 years), geographic region (US, non-US), baseline EDSS score, and baseline number of T2 lesions as covariates. Log transformed observation duration from screening MRI to last available MRI scan will be the offset variable. The estimated mean number of lesions per year for each treatment group and the corresponding two-sided 95% CI will be estimated from the negative binomial model where the adjusted mean value within treatment group is based on a sample size dependent weight within each categorical covariate (ie, weight by overall proportion of participants in each stratum or categorical factor, also called "population weight"). The relative reduction on tolebrutinib compared to placebo, its 95% CI, and p-value will be provided. No imputation for missing data due to early study withdrawal will be performed.

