4.2.1 Justification for participant's age and study duration

Male and female participants with a diagnosis of NRSPMS between 18 and 60 years inclusive will be selected for this study. The age range is limited to participants who are \leq 60 years to reduce confounding neurological conditions prevalent in older individuals (eg, degenerative pathology of the spine, vascular disorders, other neurodegenerative processes). Besides, since the SPMS phenotype is more prevalent in an older population, it was considered appropriate to set the upper age limit to 60 years.

The duration of the treatment period will vary for individual participants, depending on the time of recruitment and study end as described below. All recruited participants will be followed in the study until approximately 288 events of 6-month CDP are observed. Considering the recruitment

period of approximately 24 months and an assumed event rate (see Section 9.2), the duration of the study should be approximately 48 months, with estimated mean treatment duration of 33 to 36 months.

Participants will be encouraged to remain in the study and comply with all study visits until the EOS in the case that they discontinue the study intervention early.

To minimize possible biases in the study outcome, the study is double blinded. The blind of initial treatment will be kept from participants, any Investigator site staff, and the Sponsor until the study end.

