5.1 INCLUSION CRITERIA

Participants are eligible to be included in the study only if all of the following criteria apply:

Age

I 01. Participant must be 18 to 60 years of age inclusive, at the time of signing the informed consent.

Type of participant and disease characteristics

- I 02. The participant must have a previous diagnosis of RRMS in accordance with the 2017 revised McDonald criteria (5).
- I 03. The participant must have a current diagnosis of SPMS in accordance with the clinical course criteria (11) revised in 2013 (10) and endorsed by an Adjudication Committee.
- I 04. The participant must have documented evidence of disability progression observed during the 12 months before screening. Eligibility will be analyzed by an Adjudication Committee (to evaluate source data for disability confirmation; details see Section 10.1.5.3).
- I 05. Absence of clinical relapses for at least 24 months.
- I 06. The participant must have an EDSS score at screening from 3.0 to 6.5 points, inclusive.
- I 07. Deleted in Amended Protocol 03.

Weight

I 08. Not applicable.

Sex

I 09. Male and/or female

Contraceptive use should be consistent with local regulations regarding the methods of contraception for those participating in clinical studies.

A) Male participants

Not applicable.

- B) Female participants
- A female participant is eligible to participate if she is not pregnant or breastfeeding, and at least one of the following conditions applies:
 - Is not a woman of childbearing potential (WOCBP).

OR

- Is a WOCBP and agrees to use an acceptable contraceptive method as described in Appendix 4 (Section 10.4) during the intervention period. WOCBP must use reliable means of contraception as described in Appendix 4 (Section 10.4) at a minimum. If local requirements are more stringent than what is described in Appendix 4 (Section 10.4), they should be followed.
- A WOCBP must have a negative highly sensitive pregnancy test (urine or serum as required by local regulations) (Appendix 2 [Section 10.2]) at screening and before the first dose of study intervention.
- If a urine test cannot be confirmed as negative (eg, an ambiguous result), a serum pregnancy test is required. In such cases, the participant must be excluded from participation if the serum pregnancy result is positive.
- Requirements for pregnancy testing during and after study intervention are located in the SoA (Section 1.3).

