6.4 MEASURES TO MINIMIZE BIAS: RANDOMIZATION AND BLINDING

All participants will be centrally assigned to randomized study intervention using an interactive response technology (IRT). Randomization will be stratified by age at screening (>40, \leq 40 years) and geographic region (US versus non-US). A participant cannot be randomized more than once in the study. A participant assigned to a specific arm at randomization may be allocated, by the IRT, to several (varying) intervention numbers (and corresponding intervention kit numbers) for multiple visits despite having the same intervention arm assignment from randomization. That is, in these cases, the intervention/kit number varies but the arm assignment at randomization does not change. Before the study is initiated, the log in information and instructions for the Interactive Web Response System (IWRS) will be provided to each site.

Study intervention will be dispensed at the study visits summarized in the SoA (Section 1.3).

Returned study intervention should not be re-dispensed to the participants.

The Treating Investigator, Examining Investigator/rater, clinical site staff, and Sponsor's clinical trial team members will not have access to the randomization (treatment) codes. The IRT will be programmed with blind-breaking instructions. In case of an emergency, the Investigator has the sole responsibility for determining if unblinding of a participant's treatment assignment is

Amended Clinical Trial Protocol 12 SAR442168-EFC16645 - tolebrutinib 20-Dec-2023 Version number: 1

warranted (eg, in case of available antidote). Participant safety must always be the first consideration in making such a determination. If a participant's treatment assignment is unblinded, the Sponsor must be notified within 24 hours after breaking the blind. The date and reason that the blind was broken must be recorded in the source documentation and electronic case report form (eCRF), as applicable. If unblinded, information pertaining to the treatment allocation should not be shared with other members of the study team or Sponsor.

Methods of blinding

This study is blinded for assignment of SAR442168 and placebo. Tablets of SAR442168 and placebo will appear identical.

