#### **Analytical Approach**

The time to onset of 6-month CDP will be modeled by a Cox proportional hazards model with robust variance estimation (1). The covariates included in the model are treatment group, age at screening (>40,  $\leq$ 40), region (US, non-US), baseline EDSS score and baseline gadolinium (Gd)-enhancing T1 lesions (present, absent). The hazard ratio, its 95% confidence interval and the p-value for comparing tolebrutinib to placebo will be estimated from this model. Comparison between tolebrutinib and placebo will also be assessed by a log-rank test stratified by age at screening (>40,  $\leq$ 40 years) and region (US, non-US). Kaplan-Meier (KM) plots of the cumulative incidence rate will be provided by treatment group to depict the course of onset of 6-month CDP over time. The proportion of participants with events at given time points (eg, Months 6, 12, 18, 24, 30, ...) and median time to 6-month CDP will be calculated using the KM estimates.

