#### **Binary endpoints**

Binary endpoints include:

- Proportion of participants with CDI confirmed over at least 6 months
- Proportion of participants with CDI confirmed over at least 6 months and maintained until the EOS
- Proportion of participants with NEDA-3 at Months 18, 24, 30, 36, and EOS

A Cochran–Mantel–Haenszel (CMH) test stratifying by age at screening (>40,  $\leq$ 40 years) and region (US, non-US) will be used and the relative risk ratio on tolebrutinib compared to placebo with 95% CI will be estimated.

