#### **Count endpoints**

Count endpoints include:

- Annualized adjudicated relapse rate
- Total number of new Gd-enhancing T1-hyperintense lesions

A negative binomial model will be used to analyze total count occurring during the observation period, adjusting for treatment group, age at screening (>40,  $\leq$ 40 years), region (US, non-US), baseline EDSS score and baseline Gd-enhancing T1 lesion (present, absent). Log transformed post-randomization observation duration or number of scans will be the offset variable. The estimated mean rates/numbers for each treatment group with the corresponding 95% CI, and the relative reduction on tolebrutinib compared to placebo with the 95% CI will be estimated.

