## 5.3 APPENDIX 3 DEMOGRAPHICS AND BASELINE CHARACTERISTICS, PRIOR OR CONCOMITANT MEDICATIONS

#### Demographics, baseline characteristics, medical surgical history

The following demographics and baseline characteristics, smoking and alcohol history, disease characteristics at baseline, and medical and surgical history will be summarized using descriptive statistics in the randomized population.

Demographic and baseline characteristics

- Age in years as quantitative variable and in categories ( $\leq 40$ , >40; 18 to 60)
- Sex (Male, Female)
- Race (White, Black or African American, Asian, American Indian or Alaska Native, Native Hawaiian or Other Pacific Islander, Multiple, Unknown, Not reported)
- Ethnicity (Hispanic or Latino, not Hispanic or Latino, Unknown, Not reported)
- Region (US, non-US; North America, Western Europe, Eastern Europe, ROW)
- Weight in kg as a quantitative variable
- BMI in kg/m^2 as a quantitative variable and in categories (<25,  $\geq 25$  to <30,  $\geq 30$ )

Smoking and alcohol habits

- Smoking history (Never, Current, Former)
- Cessation prior to screening for Former smokers in months
- Cigarettes per day for smokers

- Frequency of alcohol drinking in the past 12 months (Never, Occasional, At least monthly, At least weekly, At least daily)
- # Standard alcohol drinks on typical day when drinking (1 or 2, >2)

Disease characteristics at baseline

- Time since symptom onset of relapsing-remitting multiple sclerosis (RRMS) in years
- Time since diagnosis of secondary progressive multiple sclerosis (SPMS) in years
- Time since most recent relapse in years
- Baseline EDSS score as a quantitative variable (average of screening and baseline scores when both available)
- Disease burden at baseline (baseline EDSS  $\leq$ 4.5 versus >4.5; EDSS  $\leq$ 5.5 versus >5.5)
- Baseline Gd-enhancing T1 lesion (absent, present)

Baseline safety and efficacy parameters (apart from those listed above) will be presented along with the safety and efficacy summaries.

Relevant medical (or surgical) history collected in the eCRF will be coded to a LLT, PT, HLT, HLGT, and associated primary SOC using the MedDRA version currently in effect at Sanofi at the time of database lock and will be summarized by primary SOC and HLT (internationally agreed SOC order and decreasing frequency of HLTs in the Overall group).

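### The T2-lesion and MMRM analyses adjust for age only as over 40 versus 40 or younger, although age in years is collected; adding it is a cheap, optional gain in precision

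*SAP*

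**What the plan says.** Protocol 6.4 fixes the cut: "Randomization will be stratified by age at screening (>40" versus 40 or younger), together with US versus non-US. Protocol 5.1 sets the eligible range: "Participant must be 18 to 60 years of age inclusive".

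The SAP uses the same two-level factor throughout:

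- **T2-lesion negative binomial model (3.3.1.2.2):** the lesion count enters "as the response variable, with treatment group, age at screening (>40", alongside region, baseline EDSS and baseline T2 lesion number.
- **MMRMs (3.3.1.2.3 and 3.4.2):** brain volume, SDMT, CVLT-II, MSQoL-54, MSFC-3, T2 volume and EQ-5D-5L.
- **Primary Cox model (3.2.2):** "The covariates included in the model are treatment group, age at screening (>40"; the other time-to-event analyses follow it, and the imputation model in 3.2.3 has the same term.
- **Exploratory counts (3.4.2):** "adjusting for treatment group, age at screening (>40".
- **Exploratory binary endpoints (3.4.2):** a CMH "test stratifying by age at screening (>40".

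Age in years is available. SAP 5.3 will summarize "Age in years as quantitative variable and in categories". On the expected age mix, the documents say only, in Protocol 4.2.1, that "since the SPMS phenotype is more prevalent in an older population". They give no mean, SD or share over 40, and no estimate of how age relates to any outcome.

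**The concern.** A two-level factor carries little information about age inside its larger level. If most participants are over 40, which Protocol 4.2.1 makes likely, most of the sample shares one value of the factor while ages within that level range over some 20 years. Any relation between age and outcome inside that level stays in the residual variation.

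Two of the affected analyses are in the testing hierarchy of SAP 3.5: T2 lesions stand second among the ordered secondary endpoints, and brain volume is last. A miss on T2 lesions closes the tests of 9-HPT, T25-FW, CDI and brain volume. The SAP already goes beyond the strata elsewhere: it enters baseline EDSS and baseline T2 lesion number as covariates. Age in years would be treated in the same way.

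**Working it through.** **Plan's own figure.** The documents give no figure for age adjustment. The nearest is 80% power from 288 events at HR 0.70, 2:1, two-sided 0.05. By Schoenfeld, √(288 × 2/9) × |ln 0.70| = 8 × 0.357 = 2.853, and Φ(2.853 − 1.960) = 81.4%. That agrees with the plan.

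**Step 1: age information kept by the cut.** The share kept is the squared correlation between age and the over-40 indicator. All age distributions here are assumptions: normal, truncated to 18-60, in completed years.

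| Mean, SD | 40 or younger | Age variance lost |
|---|---|---|
| 45, 8 | 32% | 38% |
| 47, 8 | 24% | 43% |
| 49, 8 | 17% | 49% |
| 50, 8 | 14% | 52% |
| 52, 8 | 10% | 59% |
| 50, 7 | 11% | 60% |
| Uniform 18-60 | 54% | 25% |

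The loss is therefore about 25-60%. It depends on how age is handled: with exact rather than completed years and an older, tighter population (95% over 40), the factor keeps only 28%, a loss of 72%. For an untruncated normal with a share p at 40 or younger, the part kept is φ(z_p)²/[p(1 − p)]. At p = 0.15 this is 0.43, a loss of 57%. More than half is lost only if fewer than about 16% (truncated, SD 8) to 21% (untruncated) are 40 or younger.

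**Step 2: MMRM-type endpoints.** Let age explain a share R² of the residual variance and the factor keep a share k of age variance. The ratio of treatment-effect variance, factor only to factor plus age, is (1 − kR²)/(1 − R²).

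- R² = 1%, k = 0.59: 0.9941/0.99 = 1.004, a 0.4% reduction.
- R² = 5%, k = 0.28: 0.986/0.95 = 1.038, a 3.7% reduction.

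From 80% power and k of 0.35-0.60, the gain is 0.1 point at R² = 0.5%, 0.3-0.5 points at 2% and 0.8-1.3 points at 5%.

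**Step 3: T2-lesion model.** Negative binomial simulation with robust standard errors, comparing the factor alone with factor plus age in years. Assumed: 1100 participants, dispersion 3, about 1 lesion per year. Two sets of runs gave these variance ratios:

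| Log-rate slope per year of age | Variance ratio | Reduction, 1 − 1/ratio |
|---|---|---|
| 0 | 1.004; 1.01 | 0.4%; 1.0% |
| −0.03 | 1.027; 1.03 | 2.6%; 2.9% |
| −0.06 | 1.079; 1.09 | 7.3%; 8.3% |

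The first row should be read as zero, because there is nothing to gain when age has no effect.

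**Step 4: Cox model.** Simulation with 1290 participants and the plan's event and dropout rates, age assumed mean 49 and SD 8, 1500 runs per setting. The linear age term replaced the factor.

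| Age HR per decade | Power, factor | Power, linear age |
|---|---|---|
| 1.0 | 84.3% | 84.4% |
| 0.8 | 85.6% | 86.0% |
| 1.2 | 85.5% | 85.9% |
| 1.5 | 83.2% | 83.0% |

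Differences are at most 0.4 points, and one is negative.

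**The case against.** The strongest reply is that nothing here is wrong. The cut at 40 is the factor used to randomize, the models adjust for it, and randomization protects the comparison. The stratified log-rank and CMH tests need categories. All of this stands.

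The assumed effects also deserve caution. Over the 42 years from 18 to 60, a slope of −0.06 implies a rate ratio of exp(2.52), about 12-fold, and −0.03 implies exp(1.26), about 3.5-fold. The T2 simulation compared age terms only. Baseline EDSS and baseline T2 lesion number are already in that model and may carry some of the age information, so the upper figure may be generous. The MMRMs likewise already adjust for the baseline value. Protocol 4.2.1 justifies an eligibility limit; it does not say that age predicts lesions, atrophy or progression within 18-60.

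Three stronger readings are tempting, and the documents do not support them:

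- *Most age information is thrown away.* That needs a share aged 40 or younger below roughly 16-21%, and the documents give no share.
- *Adding age can only help, the primary analysis included.* Step 4 shows no meaningful gain. In a Cox model an added covariate also changes the conditional hazard ratio being estimated, so the argument from residual variance does not carry over.
- *Age is handled crudely for every endpoint.* SAP 3.3.1.1 standardizes CVLT-II by sex within 7 age groups.

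What survives is narrower: in the count and linear models, a baseline value already in the database could be used at almost no cost.

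**Conclusion.** The point holds as an optional refinement, not as an error or a source of bias. The two-level factor is valid but gives up a substantial part of the age information, about 25-60% under most of the age distributions tried. The resulting gain is small: roughly 0-4% lower treatment-effect variance for the MMRMs if age explains up to 5% of residual variance, and 0-8% for the T2 model for slopes from 0 to −0.06 per year. If age is not prognostic, nothing is gained. Confidence is high on what the plan says and moderate on the size, which rests on assumed age distributions, age effects, dispersion and lesion rate. The Cox models can stay as written.

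**What to change.** Before unblinding, keep the over-40 stratification factor and add age at screening in years as a continuous covariate to:

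- the T2-lesion negative binomial model (SAP 3.3.1.2.2);
- the MMRMs for brain volume, SDMT and MSQoL-54 (3.3.1.2.3);
- the MMRMs for the exploratory continuous endpoints (3.4.2).

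The rank ANCOVA sensitivity analyses take their covariates from the MMRMs and would follow. State that adjusted means are evaluated at the overall mean age, since the SAP's population weights are defined only for categorical factors. Align the covariate lists in Protocol 9.4.3 and the synopsis, and exempt CVLT-II, which needs no change.

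Leave the Cox, log-rank and CMH analyses as they are. If age in years were nevertheless added to the primary Cox model, it would also have to enter the imputation model in SAP 3.2.3, and Protocol 9.4.2 would have to change.

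The cost is a sentence per model, the protocol alignment, one degree of freedom per model and a linearity assumption. If age does not act linearly, some efficiency is lost but the treatment comparison stays valid. No new data are needed.

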The ability of SAR442168 to reduce the formation of acute brain lesions in MS was assessed in a Phase 2b dose-finding trial in participants with relapsing MS (RMS) (DRI15928). Patients with progressive forms of MS may also present with acute focal inflammatory activity in the CNS. This activity manifests on MRI as T1 hyperintense Gd+ lesions and new or enlarging T2 lesions. SAR442168 has proven to be effective in reducing both types of CNS lesions. The SAR442168 Phase 2b results showed that SAR442168 reduced the number of new T1 hyperintense Gd+ lesions by 85% and the number of new or enlarged T2 lesions by 89% in the 60 mg group (the dose to be used in the Phase 3 program) compared to placebo.

Reduction in number of T1-hyperintense (gadolinium-enhanced) lesions has been established as a highly reliable predictive biomarker for clinical efficacy in pivotal studies in MS including Phase 3 RMS studies (3). While there is no comparable radiographic biomarker to predict clinical efficacy on disability progression, the assumption has been that doses effective at preventing relapses can be used to assess disability progression in PPMS or SPMS (2, 4, 5, 6, 7). SAR442168 was shown to achieve pharmacologically relevant concentrations in cerebrospinal fluid (CSF) after a single oral administration, with the potential to inhibit microglia and infiltrating bonemarrow-derived macrophages that are believed to drive neuroinflammation linked to disease progression.

The goal of this Phase 3 clinical trial is to demonstrate the efficacy and safety of SAR442168 compared to placebo in participants with nonrelapsing secondary progressive multiple sclerosis (NRSPMS). The primary endpoint is time to onset of 6-month CDP assessed via the Expanded Disability Status Scale (EDSS) score.

The EDSS is widely used to measure neurological disability in clinical trials and routine settings (8). It will be used to assess 6-month CDP, as is standard practice in many clinical trials and as is recommended by guidelines (2, 4) and considered as more stable than 3-month CDP. Electronic EDSS score collection will be employed to ensure completeness and consistency of measurement. Magnetic resonance imaging outcomes will include change in brain volume, which is considered as a marker of the CNS degenerative process and therefore recommended for use in progressive MS trials (9).

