9.4.3 Secondary endpoint(s)

For other time-to-event endpoints (time to onset of sustained 20% increase in the 9-HPT, of sustained 20% increase in the T25-FW, of 3-month CDP, and of CDI), similar analysis as for the primary analysis of the primary efficacy endpoint will be performed in the ITT population but without imputation.

Continuous endpoints (percent change in brain volume loss, change in cognitive function, change in physical function, and change in MSQoL-54 at EOS) will be analyzed using a mixed-effect model with repeated measures (MMRM) approach. The model will include change/percent change values for the respective endpoint at each scheduled visit as response variables, and treatment, age at screening (>40, \leq 40 years), geographic region (US, non-US), visit, treatment by-visit interaction, baseline value for the endpoint being assessed and baseline value-by-visit interaction as covariates. Difference in LS means, the corresponding 95% CI, and p-value will be provided for the comparison of SAR442168 versus placebo. For percent change in brain volume loss, log transformation will be applied in the MMRM model. In order to assess the impact of deviation from the normality assumption, a sensitivity analysis using rank ANCOVA with the same covariates as for the MMRM analysis except visit and related interaction terms, will be performed for these continuous endpoints to provide the p-value for the comparison between the treatment groups.

Categorical efficacy endpoints with count data (new and/or enlarging T2 hyperintense over the study period after baseline) will be analyzed using a negative binomial regression model. The model will include the total lesion count across all post-randomization MRI scans during the study period as the response variable, with treatment group, age at screening (>40, \leq 40 years), geographic region (US, non-US), baseline EDSS score, and baseline T2 lesions as covariates. Log-transformed observation duration from screening MRI to last available MRI will be the offset variable. In order to assess the impact of open-label therapy, sensitivity analysis excluding the data after initiation of open-label therapy will be performed for the key secondary endpoints that will be pre-specified in the SAP. Further details including details of missing data handling and subgroup analyses for secondary endpoints will also be detailed in the SAP.

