## **3 STATISTICAL ANALYSES**

#### 3.1 GENERAL CONSIDERATIONS

The baseline values of efficacy parameters are generally defined as the last available value prior to the first dose of study medication unless otherwise specified. In most cases the assessment should be prior to the randomization call, but it is possible that some assessments are performed between the actual randomization call and the first intake of investigational medicinal product (IMP). For the Expanded Disability Status Scale (EDSS) score, the baseline value will be taken as the average of the screening and randomization visit values. If one of the values is missing, the non-missing value will be used as baseline. The baseline value of safety parameters is defined as the last available value prior to the first dose of IMP. For the C-SSRS, the baseline value will be the worst assessment between the past 6 months evaluation at screening and the C-SSRS since last visit evaluation on Day 1. For participants randomized but not treated, the baseline value is defined as the last available value before randomization. Unless otherwise indicated, 2-sided p-values and 95% confidence intervals (CIs) will be provided for treatment comparisons.

To include all participants in analyses where baseline Gd-enhancing T1-hyperintense lesion presence or absence is used as a covariate, baseline status (present or absent) will be imputed for participants with a missing baseline count: if subsequent post-baseline counts for a participant are all 0, then impute baseline status as absent, otherwise, impute baseline status randomly with seed = 16645 based on the proportion of presence/absence at baseline in the overall population. Of note, the number of participants affected is minimal with no impact on results.

In general, continuous data will be summarized using the number of observations available, mean, standard deviation (SD), median, interquartile range (Q1, Q3), minimum, and maximum. Categorical and ordinal data will be summarized using the count and percentage of participants. Efficacy data will be analyzed in the ITT population, and safety data will be analyzed in the safety population, unless specified otherwise.

Unless otherwise specified, analyses will be performed by treatment group and overall for baseline and demographics characteristics.

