### 3.3.1.2 Main analytical approach

#### 3.3.1.2.1 Time to event endpoints

Time to onset of 3-month CDP will be analyzed using the same statistical methods as for the primary analysis of time to onset of 6-month CDP without imputation.

Time to onset of sustained 20% increase in the 9-HPT (T25-FW) for at least 3 months and time to onset of 6-month confirmed disability improvement (CDI) will be analyzed using similar statistical methods as for the primary analysis of time to onset of 6-month CDP, but without imputation. Participants with onset without confirmation will be treated as censored at the last endpoint assessment.

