Change from baseline in SDMT number of correct substitutions, CVLT-II total correct and MSQoL-54 physical and mental health composite scores at the EOS will be analyzed using an analogous MMRM approach in the ITT population with the change from baseline values for the respective endpoint at scheduled visits up to and including the EOS visit as response variables, and treatment group, age at screening (>40,  $\leq$ 40 years), geographic region (US, non-US), visit, treatment-by-visit interaction, baseline value for the endpoint being assessed and baseline value-by-visit interaction as covariates.

For each endpoint, difference in LSM, the corresponding 95% CI, and p-value will be estimated from the MMRM model for the comparison of tolebrutinib to placebo using weights for each stratum equal to the overall proportion of participants in each stratum (ie, "Population weight"). Plots of LSM [±standard error (SE)] over time will be provided. Participants who discontinue study intervention before the study end will be asked and encouraged to return for all remaining study visits and the additional off-treatment values measured up through the EOS will be included in the primary analysis. For participants who withdraw from the study before the EOS, values will be missing after study discontinuation and no imputation will be performed.

SDMT, CVLT-II and MSQoL-54 data are assumed a priori to be normally distributed. Given the large sample size, the impact of violation of normality should not be great. In order to assess the impact of deviation from the normality assumption, a sensitivity analysis using rank analysis of

covariance (ANCOVA), with the same covariates as for the MMRM analysis except VISIT and related interaction terms, will be performed to test the significance of the treatment effect.

Given that participants who reach the primary endpoint of 6M-CDP are eligible to switch to OL tolebrutinib, including data after the switch could impact the analysis of secondary endpoints: number of new/enlarging T2 lesions per year, time to onset of sustained 20% increase in the 9-HPT (T25-FW) for at least 3 months, and percent change in brain volume at EOS compared to Month 6. Sensitivity analyses excluding data after initiation of OL therapy will be performed for these endpoints.

No other sensitivity, supplementary, or subgroup analyses will be performed for the secondary endpoints.

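### The confirmatory T2-lesion model is valid, but it omits baseline Gd-enhancing lesion status, which could add precision at almost no cost

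*SAP*

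**What the plan says.** SAP 3.3.1.2.2 fits a negative binomial regression with robust variance to each participant's total new or enlarging T2 lesions, with log time from screening MRI to last MRI as offset. The adjusters are age stratum, region, "baseline EDSS score, and baseline number of T2 lesions as covariates". Protocol 9.4.3 and the synopsis have the same set, ending "baseline EDSS score, and baseline T2 lesions as covariates".

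Baseline Gd status is used elsewhere:

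- The primary Cox model (SAP 3.2.2) includes "baseline EDSS score and baseline gadolinium (Gd)-enhancing T1 lesions (present, absent").
- The time-to-event secondaries inherit it (SAP 3.3.1.2.1): "Time to onset of 3-month CDP will be analyzed using the same statistical methods as for the primary analysis". The 9-HPT, T25-FW and CDI analyses use similar methods.
- The exploratory count models for relapse rate and new Gd lesions (SAP 3.4.2) include it.

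It is not universal. The brain-volume, T2-volume and CMH analyses leave it out.

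SAP 3.1 fills in a missing baseline Gd status: "if subsequent post-baseline counts for a participant are all 0, then impute baseline status as absent"; otherwise the status is drawn at random from the overall baseline proportions. The SAP calls the number affected minimal.

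The only other planned analysis of this endpoint excludes data after the switch to open-label treatment. SAP 3.3.1.2.3 then closes the list: "No other sensitivity, supplementary, or subgroup analyses will be performed for the secondary endpoints".

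**The concern.** The synopsis rationale describes acute focal inflammation in progressive MS as follows: "This activity manifests on MRI as T1 hyperintense Gd+ lesions and new or enlarging T2 lesions". Baseline T2 count measures accumulated lesion burden, whereas Gd enhancement marks current activity. On the protocol's own account, then, Gd status may predict new T2 lesions beyond the T2 count. Omitting a predictive baseline variable from a count model does not bias the rate ratio in a randomized trial, but it leaves avoidable between-participant variation and a wider confidence interval.

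The endpoint is second among the secondaries in the fixed sequence (SAP 3.5). If it misses the 5% level, 9-HPT, T25-FW, CDI and brain volume cannot be formally tested.

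**Working it through.** **The plan's own figure.** The only power statement concerns the primary endpoint: about 288 events for 80% power at a hazard ratio of 0.70 with 2:1 allocation. By the Schoenfeld formula, power at 288 events is Φ(|ln 0.70| × √(288 × 2/9) − 1.96) = Φ(0.3567 × 8 − 1.96) = Φ(0.893) = 81%, which agrees. It does not bear on the T2 endpoint, for which no power, lesion rate or dispersion is given.

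**Inputs from the documents.** N up to 1290, or about 1100 with longer follow-up; 2:1 allocation; 24 months' enrollment; last participant followed 24 months (30 for N=1100); 10% annual discontinuation; two-sided 5%.

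**Assumed inputs.**

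- Gd-positive prevalence 5% or 12.5%, correlated with T2 count (log-odds 0.5 per SD).
- Gd rate ratio R from 1 to 4, conditional on T2 count.
- T2-count effect 0.35 per SD on the log rate.
- 0.8 lesions per year in the placebo, Gd-negative, reference-age group.
- Dispersion 1.0 or 2.5.
- Treatment rate ratio 0.70.

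**Why precision changes.** For a negative binomial count with mean μ and dispersion k, each arm contributes (1/μ + k)/n to the variance of the log rate ratio. Leaving out a binary predictor with prevalence p and rate ratio R inflates dispersion to (1+k)(1+c) − 1, where c = p(1−p)(R−1)²/(1−p+pR)².

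Example without the T2 covariate: p = 0.10, R = 2, k = 1, placebo mean 1.5 lesions, 430 placebo and 860 active.

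- c = 0.09/1.21 = 0.0744, so marginal dispersion is 2 × 1.0744 − 1 = 1.149.
- Variance without Gd: (1/1.5 + 1.149)/430 + (1/1.05 + 1.149)/860 = 0.00422 + 0.00244 = 0.00667.
- With Gd, the stratum means on placebo are 1.364 and 2.727. The stratum variances are 0.00712 and 0.0495, so the combined variance is 1/(140.4 + 20.2) = 0.00623.
- Ratio 0.00667/0.00623 = 1.07.

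Over p = 5–20%, k = 1–4 and 0.5 or 1.5 lesions per year for 3 years, this ratio is 1.00 at R = 1, 1.04–1.16 at R = 2 and 1.32–1.79 at R = 4.

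**Simulation with T2 count in both models.** There were 1500 trials per scenario, with age, region and EDSS also in both models, a log-time offset and sandwich variance. The table is for 12.5% Gd-positive and dispersion 2.5. Power is Φ(0.3567/SE − 1.96).

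| N | R | SE without Gd | SE with Gd | Fall in SE | Power without | Power with |
|---|---|---|---|---|---|---|
| 1290 | 1 | 0.1077 | 0.1076 | 0.1% | 91% | 91% |
| 1290 | 1.5 | 0.1083 | 0.1071 | 1.1% | 91% | 91% |
| 1290 | 2 | 0.1108 | 0.1066 | 3.8% | 90% | 92% |
| 1290 | 3 | 0.1184 | 0.1063 | 10.2% | 85% | 92% |
| 1290 | 4 | 0.1271 | 0.1060 | 16.6% | 80% | 92% |
| 1100 | 1 | 0.1150 | 0.1149 | 0.1% | 87% | 87% |
| 1100 | 2 | 0.1184 | 0.1142 | 3.5% | 85% | 88% |
| 1100 | 4 | 0.1366 | 0.1136 | 16.8% | 74% | 88% |

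Across both prevalences and both dispersions at N=1290, the SE falls by 0.0–0.1% (R = 1), 0.6–1.3% (1.5), 2–4% (2), 6–12% (3) and 11–19% (4). With dispersion 1.0 power is at least 96% either way. The mean estimated rate ratio was 0.70 with and without Gd in every scenario.

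**Cross-checks.** A separate simulation (dispersion 2, 1 lesion per year, 10% Gd-positive) gave power of 94.8% to 95.7% at R = 2 and 84.0% to 95.7% at R = 4. Under no treatment effect (R = 4) it rejected 5.0% without Gd and 4.5% with it. A rerun of the main setup at 4-fold and dispersion 2.5 gave 78% to 92% with 12.5% Gd-positive and 82% to 90% with 5%.

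**When the effect is larger.** At the largest SE above, a 50% reduction has power Φ(0.693/0.1366 − 1.96) = Φ(3.11), over 99%. The reduction detectable with 90% power is 1 − exp(−3.24 × SE), where 3.24 = 1.96 + 1.28. For N=1100 and R = 4 this is 36% without Gd and 31% with it.

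**The case against.** The strongest reply is that this is a preference, not a defect. Amendment 10 revised both models together: it gave the Cox model EDSS and Gd status, and the T2 model EDSS and T2 count. The lesion endpoint therefore got its own baseline measure, as most of the continuous-endpoint models do. Every input that sets the size of the gain is assumed, and several (lesion rate, T2 effect, Gd–T2 correlation) are single values in the main simulation. The 30% reduction is borrowed from the primary endpoint. The only T2 effect in the documents is an 89% reduction in relapsing MS, where power would not be in question. The missing-value rule would also bring post-randomization Gd counts into a confirmatory model now free of them, and a protocol change carries administrative work.

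Much of this stands. The plan contains no error, the gain is small at R = 2 or below, and for a large effect it is immaterial. It does not remove the case for the change. The amendment gives no reason against Gd status. The 89% figure is from another population, and the main analysis here keeps data after placebo participants switch to open-label tolebrutinib, which would be expected to dilute the contrast. The missing-value rule already governs every Gd-adjusted analysis. Nothing measurable is lost if Gd status proves uninformative.

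**Conclusion.** The point holds as an efficiency improvement, not as the correction of an error. The planned T2 analysis is valid and showed no material bias. Adding baseline Gd status costs essentially nothing if it is uninformative, and cuts the standard error by 2–4% at a 2-fold and 11–19% at a 4-fold Gd rate ratio (N=1290). The gain in power matters only for a modest treatment effect combined with high dispersion and a strong Gd association. All these sizes rest on assumed prevalence, rate ratio, lesion rate and dispersion. Worth doing because four further endpoints depend on this test; confidence in a material gain is medium.

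**What to change.** Before unblinding, add baseline Gd-enhancing T1 lesions (present, absent) to the model in SAP 3.3.1.2.2, and align Protocol 9.4.3 and the synopsis. Apply the SAP 3.1 missing-value rule, and state in the SAP that for the few participants without a baseline value (for example, those with a contraindication to contrast, who may enroll under the note to E 12) the rule draws on post-baseline Gd counts. Imputing from baseline data only would avoid this in the T2 model.

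The cost is one covariate in one model statement plus matching text; no new data are needed. It does require a further SAP version and a protocol text change. There is a precedent for order: SAP version 1 specified the added Cox covariates before Amendment 10 brought them into the protocol.
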